- Number of circumferential extremity wounds per patient

- Interstitial pressure (mmHg) for circumferential extremity wounds (on a wound level)
- Criteria for inclusion (met/not met)
- Counts of patients/wound per strata (%TBSA cut point 15%, depth cases 1-3, center)

will be analyzed descriptively with number of units, number of missing values, mean, standard deviation, min, max, median and quartiles in case of numeric values and counts and percentages in case of categorical items to describe the study population. The analysis will be done by treatment group and in total.

The descriptive results for all variables will be tabulated. Exemplary tables are presented in Section 13.2. Histograms will be produced for each continuous variable, bar plots for categorical variables. Figures can be seen in Section 13.3.

If any of the baseline factors, gender, age, percent SPT area (the area of SPT as a percentage of the total area of all TWs, classified as <25% or ≥25%), time from injury to randomization or number of TWs (1, 2, ≥3) are found to be significantly different between the treatment groups (Chi-squared tests (or in case of small estimated cell counts Fisher's exact test) for categorical variables and one-way analysis of variance for continuous variables) then the factor will be included as an extra adjusting covariate in the supportive analysis models for the primary and secondary efficacy endpoints and the comparative analyses of safety endpoints.

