11.1.3. Secondary Efficacy variables

The secondary endpoints will be analyzed as described below and will compare efficacy in the NexoBrid group with the SOC group. Missing data will be handled by the methods described in Section 10.1. All secondary endpoints will be analyzed using the FAS. Sensitivity analyses will include analyzing the endpoints using the PP as analysis population.

11.1.3.1. *Incidence of surgical excision*

This is a binary yes/no variable and the proportion of patients who need excision for eschar removal will be compared using logistic regression. The explanatory variables in the model will include treatment, and the following variables: overall TW depth (all TWs full thickness, mixed TWs, all TWs deep partial thickness), “Total %TBSA per patient” and number of TWs (1, 2, ≥3). The odds ratio of requiring surgery for NexoBrid versus SOC will be estimated from the model, as well as 95% confidence intervals and the level of statistical significance. The results

will be displayed as shown in Table 6 and Table 7. Bar plots will be shown for the proportions of patients who needed excision for eschar removal.

If numerically possible, as a supportive analysis, the variable treatment center will be added into the logistic regression model and the analysis repeated.

As a sensitivity analysis, the logistic regression outlined above will be repeated using the PP as analysis population.

If any of the baseline factors, gender, age, percent SPT area (the area of SPT as a percentage of the total area of all TWs, classified as <25% or ≥25%), time from injury to randomization or number of TWs (1, 2, ≥3) are found to be significantly different between the treatment groups, then the factor will be included as an extra adjusting covariate in the logistic regression model described above as additional analysis.

As supportive analysis, the incidence of surgical excision for eschar removal will be compared between NexoBrid and Gel Vehicle using the same explanatory variables as in the main analysis of this endpoint.

A further supportive analysis will repeat the analysis (NexoBrid versus SOC) as described above, but on a wound level. I.e. a mixed logistic regression model with explanatory variables treatment, TW depth, %TBSA per wound and number of TWs and a random effect for patient will be performed.

11.1.3.2. *Time to complete eschar removal*

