Time until complete eschar removal will be defined as the time until complete eschar removal has been achieved at a patient level, i.e. for all TW's of an individual patient. This will be measured as time from the randomization date (hours). For patients who do not reach complete eschar removal, their time will be censored at the last non-missing eschar removal assessment (typically the last debridement procedure). Kaplan-Meier curves will be presented graphically (see Figure 3) and in a table (see Table 8) to display the distribution of time to complete eschar removal under the two treatments (NexoBrid vs. SOC). Median time to complete eschar removal will be estimated for each treatment group with a 95% confidence interval. Additionally, time to complete eschar removal will be analyzed descriptively with number of units, number of missing values, mean, standard deviation, min, max, median and quartiles as presented in Table 4. The treatment groups will be compared using a Cox regression model. The comparison will be adjusted for the explanatory variables overall TW depth (all TWs full thickness, mixed TWs, all TWs deep partial thickness), "Total %TBSA per patient", center group (as defined in Section 11.1.10) and number of TWs (1, 2, ≥3), by

including each of them in the Cox regression model together with the treatment variable (NexoBrid vs. SOC). The results of the regression analysis will be displayed as in Table 7. The treatment groups will be compared by testing the null hypothesis of no difference, comparing the ratio of the estimated treatment coefficient to its standard error to a standard normal distribution.

The Cox Regression analysis outlined above will be performed if the proportional hazards assumption appears to hold. This will be checked by including in the regression model a variable representing the interaction between time since randomization and treatment group. If the coefficient for this time variable is non-significant at the 5% significance level, then the Cox Regression analysis will be adopted. If the time-treatment group interaction is significant, then a generalized Wilcoxon-Gehan test will be performed using the *Wilcoxon* option (also provided by default) in the SAS procedure PROC LIFETEST using the following SAS Code:

```
PROC LIFETEST DATA=burn_data;
  TIME time*status(0);
  STRATA depthgroup numtw tbsagroup centergroup / GROUP = treatment_group;
  RUN;
```

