Here *burn_data* is the data set containing all necessary information. The variable *time* is the time to complete eschar removal, *status* is a censoring variable and *depthgroup*, *numtw*, *tbsagroup*, and *centergroup* are the variables, which is adjusted for. *Depthgroup*, *tbsagroup* and *centergroup* are the stratification levels defined in Section 11.1.10 and *numtw* is the number of target wounds (1, 2, ≥ 3).

As sensitivity analysis the procedure outlined above will be repeated using the PP instead of the FAS as analysis population.

Supportive analyses will include adjustment for other baseline variables that are imbalanced (i.e. gender, age, percent SPT area [the area of SPT as a percentage of the total area of all TWs, classified as $<25\%$ or $\geq 25\%$], time from injury to randomization or number of TWs (1, 2, ≥ 3)), and investigating interactions between those variables and the treatment groups. In case the proportional hazards assumption could not be rejected, this will be done by including each of the imbalanced baseline variable as well as the interaction between that variable and the treatment group in a separate cox regression analysis. The results of these analyses will be presented as in Table 7. In case the proportional hazards assumption does not hold, the adjustment for the baseline variables will be done using the following SAS code:

```
PROC LIFETEST DATA=burn_data;
TIME time*status(0);
STRATA depthgroup numtw tbsagroup centergroup gender agegroup sptgroup /
GROUP = treatment_group;
RUN;
```

Here burn_data is the data set containing all necessary information. The variable time is the time to complete eschar removal, status is a censoring variable and depthgroup, numtw, tbsagroup, centergroup, gender, agegroup and sptgroup are the variables, which is adjusted for. Agegroup is the categorical age variable computed in Section 10.1.1.2, depthgroup, tbsagroup and centergroup are the stratification levels defined in Section 11.1.10 and numtw is the number of target wounds (1, 2, ≥ 3).

Another supportive analysis will be the comparison of treatments based on the time of complete eschar removal measured from the date of ICF using the same methods as for the time measured from randomization.

Another supportive analysis will be the comparison of treatments based on the time of complete eschar removal measured from the date of injury using the same methods as for the time measured from randomization.

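### The supportive Cox models that adjust time to complete eschar removal for an imbalanced factor also contain its treatment interaction, so under reference or uncentred coding the treatment row is not the adjusted overall effect

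*SAP*

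**What the plan says.** SAP 11.1.3.2 sets two aims in one sentence. The first is adjustment: "Supportive analyses will include adjustment for other baseline variables that are imbalanced". The second is "investigating interactions between those variables and the treatment groups". The factors are gender, age, SPT group, time from injury to randomization and number of target wounds.

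When proportional hazards is not rejected, both aims are met by "including each of the imbalanced baseline variable as well as the interaction between that variable and the treatment group in a separate" Cox analysis. On reporting it says: "The results of these analyses will be presented as in Table 7". Table 7 (13.2) is a general layout with estimate, standard error, test, p-value and confidence limits for each variable. The section gives no coding, no centring and no contrast averaged over factor levels. It describes no supportive Cox model with the imbalanced factor as a main effect only.

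The general rule in 11.1.1 is different. For a significantly imbalanced factor, "the factor will be included as an extra adjusting covariate in the supportive analysis models for the primary and secondary efficacy endpoints". It mentions no interaction. For surgical excision, 11.1.3.1 follows that rule: "then the factor will be included as an extra adjusting covariate in the logistic regression model described above as additional analysis".

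**The concern.** This supportive analysis should tell the reader whether the NexoBrid versus SOC result on the third test in the hierarchy (11.1.8) survives adjustment for a chance imbalance. Once the interaction is in the model, the coefficient labelled treatment answers another question: the effect in one level of the factor, or at value zero. Its value depends on which level serves as reference, and it is less precise than an adjusted overall effect. Someone comparing it with the main Cox result could take a shift, or a wider interval, as the consequence of adjustment when it comes only from the parameterization. Table 7 would show the interaction coefficient too. The effect at the other level could then be added up by hand, but its confidence interval and p-value could not, because the covariance is not shown.

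**Working it through.** **1. What the treatment row estimates.** Write the log hazard as b1·T + b2·X + b3·T·X, with T for treatment and X for the factor. The treatment log hazard ratio at X = x is b1 + b3·x, so b1 is the effect at X = 0. For gender, SPT group or grouped age that is the reference level. For time from injury in uncentred hours it is zero hours. The row has an overall, average-type meaning only if b3 = 0 or if X is centred or effect-coded. With reference or uncentred coding, its standard error is larger even when b3 = 0.

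**2. Inputs from the plan.** SAP 9.3 gives a target log hazard ratio of −1.37 + 0.28/2 = −1.23, which reproduces; only its size, 1.23, is used here. Event proportions are 0.595 and 0.728 (9.3), with 75 patients per arm (9.3.1). Expected events: 75 × 0.595 + 75 × 0.728 = 44.6 + 54.6 = 99.2.

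**3. Precision with the factor as a main effect only.** From the relation behind the plan's event formula, SE ≈ √(4/99.2) = 0.201. Then z = 1.23/0.201 = 6.1.

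**4. Precision of the treatment row with the interaction, binary factor.** Only patients at the reference level inform b1, so the SE grows by about 1/√(reference share). The shares below are assumptions.

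| Share at reference | Inflation | SE | z at 1.23 | Chance of p < 0.05 |
|---|---|---|---|---|
| 50% | 1.41 | 0.284 | 4.33 | Φ(4.33 − 1.96) ≈ 99% |
| 30% | 1.83 | 0.367 | 3.35 | Φ(3.35 − 1.96) ≈ 92% |

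A simulation (800 trials per setting, 75 per arm, about 104 events, no true interaction) agrees. The SE was 0.22 with the main effect only, 0.30 at a 50% reference share (significant in 99%) and 0.39 at 30% (91%). At an assumed log hazard ratio of 0.6, about half the target, significance fell from about 82% to 51% and 36%.

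A second simulation (60 replicates per setting) used a factor present in 45% of one arm and 25% of the other. Without interaction, the SE was 0.22 for the main-effect model, 0.257 for the reference-coded interaction model and 0.221 for the centred one. The loss therefore comes from the coding.

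**5. Shift in the estimate if an interaction exists.** In the second simulation, an interaction of −0.6 gave 1.09 from the main-effect model and 1.25 from the reference row. An interaction of −1.0 gave 1.00 and 1.30.

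**6. A continuous factor left uncentred.** The inflation is about √(1 + (mean/SD)²). The SAP gives neither mean nor SD for time from injury to randomization. As an assumed range, mean = SD gives √2 = 1.41, and mean = 2 × SD gives √5 = 2.24.

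**7. Comparison within the SAP.** For the primary endpoint (11.1.2), surgical excision (11.1.3.1), blood loss (11.1.3.3) and time to wound closure (11.1.4.1), an imbalanced factor is an added covariate without interaction. The non-proportional branch of 11.1.3.2 also adjusts, by strata, without interaction. Only the Cox branch departs from the rule in 11.1.1.

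**The case against.** - **Age in years.** A reader might infer a dramatic loss of precision from age. With an assumed mean of 40 and SD of 15, the inflation would be √(1 + (40/15)²) = 2.85. Simulated SEs were about 0.64 against 0.22, and only about half of trials stayed significant at the target effect. The SAP does not support this as the expected case. Section 10.3.3.2 derives, for this endpoint, a two-level age variable cut at 35 years, the adult median in the previous study. The analysis of variance in 11.1.1 tests for imbalance and does not fix the form of age in the Cox model. What stands is that the grouped age is named only in the LIFETEST code, so its form in the Cox branch is open.
- **An adjusted effect that is never estimated.** A reader might infer this too, and it goes too far. Number of target wounds is already a main effect in the main Cox model, and 11.1.1 gives a general covariate rule that covers this endpoint. The defect is that the specific instruction in 11.1.3.2 does not carry out that rule for the other four factors.
- **No stated misreading.** The SAP does not say that the treatment row will be taken as the adjusted result. The test "comparing the ratio of the estimated treatment coefficient to its standard error to a standard normal distribution" is specified for the main model. An interaction model does serve the second aim, and effect coding or centring would remove the problem. All of that is fair, but the text puts both terms in one model, prescribes neither coding nor centring, and offers no other output for the first aim.

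**Conclusion.** The point holds as a minor specification fault. For gender, age, SPT group and time from injury to randomization, the Cox branch of 11.1.3.2 does not deliver the adjusted overall effect that 11.1.1 intends, if factors are reference-coded or continuous factors are uncentred. For a binary factor split evenly, the treatment row has an SE about 1.4 times too large. At the plan's target effect that rarely changes the conclusion; at about half the target it often would. For time from injury the inflation depends on a mean and SD that the SAP does not give.

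The consequence is confined to supportive analyses that run only after a significant baseline imbalance and when proportional hazards is not rejected. The confirmatory Cox test and the hierarchy are unaffected. The algebra needs no assumption beyond the coding; the sizes rest on the assumed reference shares, exponential times and independent censoring.

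**What to change.** In 11.1.3.2, replace the single model per imbalanced factor by two:

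- (a) The main Cox model plus the imbalanced factor as a main effect only. Report its NexoBrid versus SOC hazard ratio, confidence interval and p-value as the adjusted result.
- (b) The same model plus the treatment-by-factor interaction, with any continuous factor centred. Report from it only the interaction test and the level-specific hazard ratios.

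For number of target wounds, (a) is already the main analysis, so only (b) is needed. State whether age enters as the two-level variable of 10.3.3.2 or as continuous. The cross-reference for that variable in 11.1.3.2 points to 10.1.1.2 and should be corrected at the same time. The cost is a few sentences of SAP text and one extra model per imbalanced factor, with no new data.

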7.1.2. Intended dosage and duration of treatment

7.1.2.1. *NexoBrid*

Two grams or five grams of NexoBrid sterile powder are mixed in 20 grams or 50 grams of sterile Gel Vehicle (ratio of 1:10), respectively to obtain sterile NexoBrid Gel. NexoBrid Gel is applied to the burn wound at a dose of 2 g NexoBrid sterile powder mixed with 20g sterile Gel Vehicle per 1% of TBSA (~ surface of an adult palm) for four hours (or 5 g NexoBrid sterile powder mixed with 50g sterile Gel Vehicle per 2.5% of TBSA). The NexoBrid powder and the Gel Vehicle are to be mixed at the patient bedside ≤ 15 min prior to use.

NexoBrid should not be applied to more than 15% TBSA in one session.

NexoBrid may be applied for a second time to the same burn area, if eschar removal from the target wound after the first application is not complete but at least 50% of the eschar was removed during the first application. NexoBrid may only be applied twice to the same burn wound area.

7.1.2.2. *Gel Vehicle*

Twenty (20) grams or 50 grams of sterile Gel Vehicle will be applied on the burn skin. Gel Vehicle is applied to the burn wound at a dose of 20 grams sterile Gel per 1% of TBSA (~ surface of an adult palm) or 50 grams per 2.5% TBSA for four hours.

Gel Vehicle should not be applied to more than 15% TBSA in one session.

Gel Vehicle may be applied for a second time to the same burn area, if eschar removal from the target wound after the first application is not complete but at least 50% of the eschar was removed during the first application. The Gel Vehicle may only be applied twice to the same burn wound area.

7.1.2.3. *Standard of Care*

No more information on intended dosage or duration of treatment was specified in the protocol for the Standard of Care arm than that already given in Section 7.1.1.2.

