7.2. Trial schedule

The healing and care of the burn wound may be divided into the three distinctive phases:

1. Eschar removal treatment phase (until complete eschar removal)
2. Wound management (until complete wound closure)
3. Scar modulation and maturation

These phases are common to the care of all wounds and are well defined in acute wounds such as burns.

In this study, these phases and their treatment strategy are equal for all arms, NexoBrid, SOC, and Gel Vehicle, following the ABA white paper recommendations [24].

The total duration of the study treatment and follow up period of each participating subject is expected to be 25 months: following the Eschar removal procedure, each subject will be followed up weekly (Weeks 1, 2, 3 and 4 etc.) until complete wound closure is achieved and 2 weeks later for wound closure confirmation, for each of the subject's TWs. Long-term follow-up visits will be performed at 1, 3, 6, 12, 18 and 24 months post last wound closure confirmation visit (for details see Table 1).

Table 1: Treatment flow chart - all arms³

If applicable
 * Weekly FU assessments will be performed every 7± 2 days from start of treatment until complete wound closure. Long-term FU will be performed 1,3,6,12,18 and 24 M after last wound closure confirmation.
 **First treatment session will include any procedure for eschar removal: the NexoBrid®/Gel Vehicle/Surgical or non-surgical procedure, as per randomization arm
 ** Procedure can be either surgical or non-surgical. A whole period of continuous dressing changes (from first coverage application to last coverage application) is considered as one non-surgical procedure, assessments should not be repeated for each dressing change; Pre procedures assessments refer only to surgical procedures. Post procedures assessments refer to any surgical procedures and for non-surgical procedure only if it is the last procedure

Parameter	Screening tests	Baseline within 1 h Pre First treatment session - All arms	Topical arms (NexoBrid or Gel Vehicle): (refer to first and second application). S=Soaking, R=Removal	SOC procedures** (including additional procedures in the topical arms)	Daily assessments	Management & Re-admissions ⁴ - surgical procedures assessment	Wound	HD or premature discontinuation visit	Weekly FU*	Long-Term FU (1, 3, 6,12,18 & 24 months)*
Inform Consent signing	X									
Medical history	X									
Burn History ⁵	X									
ConMeds & AEs	X	X	X	X	X	X	X	X	X	X

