9.2. Secondary Endpoint: Incidence of surgical excision

Estimated proportions having surgical excision from study MW2004-11-02: NexoBrid 0.22; SOC 0.62

Standard errors: NexoBrid 0.048; SOC 0.054

Difference = 0.40; Standard error of difference = 0.072

Anticipated difference: $0.40 - 0.072/2 \approx 0.36$

We therefore take the anticipated proportion with complete excision to be: NexoBrid 0.24 and SOC 0.60.

Using Fisher's exact test, the sample size needed to achieve 90% power using a two-sided significance level of 5% is **86**: 43 in the NexoBrid group and 43 in the SOC group.

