10.3.3.3. Secondary Endpoint: Blood loss

10.3.3.3.1. Blood loss for main analysis

For each patient and each procedure carried out to remove eschar the estimated blood volume (EBV) will be calculated as

$$EBV = 70 \frac{cm^3}{kg} * weight(kg)$$

Furthermore, the total volume of whole blood and packed red blood cells (PRBC) transfused (in milliliters) will be calculated per procedure (transfusions given during the procedure and 4 hours \pm 15 minutes later) and denoted by V_{WB} and V_{PC} in the following.

From these quantities, the blood loss (Actual Blood Loss, ABL) will be calculated using the following formula [25]:

$$ABL = \frac{EBV * (Hb_{before} - Hb_{after})}{(Hb_{before} + Hb_{after})/2} + V_{WB} + \frac{5}{3}V_{PC}$$

The factor of 5/3 is derived from chapter 5 of Transfusion Medicine, 4th Edition [31] and compensates for the fact that equal volumes of whole blood and packed red blood cells are not comparable.

The ABL will be summed over all procedures carried out to remove eschar, with the Hb measured immediately before each procedure and 4 hours after its completion. The amount of blood transfused will be summed over all transfusions carried out during the debridement procedure and 4 hrs later i.e. the before-after periods that are spanned by these Hb measurements.

Additionally, blood loss will be computed considering the whole debridement process as one continuous procedure. For this value, the formula for ABL given above will also be used. However, the ABL will be computed using the Hb measured immediately before the first procedure and 4 hours after completion of the last procedures. The amount of whole blood and packed red blood cells (PRBC) transfused will be calculated as before, but incorporating all such transfusions in the time frame spanned by the Hb measurements used for the calculation (pre first procedure to 4 hrs post last procedure (in which complete debridement was achieved).

Analyses with both blood loss values will be conducted. However, some missing values are expected. The analysis with less missing values will be regarded as more reliable and is therefore considered the main analysis. The other analysis is considered supportive.

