10.3.3.3.5. Course of debridement procedure

For the multiple imputation outlined in Section 10.1.1.3 for each patient a categorical variable describing the course of the debridement process will be calculated. The different levels of the variable are defined as:

- Only non-surgical SOC debridement
- Non-surgical SOC debridement followed by surgical debridement
- Only surgical debridement
- Only NexoBrid debridement
- NexoBrid debridement followed by non-surgical SOC debridement followed by surgical debridement
- NexoBrid debridement follow by surgical debridement
- Only Gel Vehicle debridement
- Gel Vehicle debridement followed by non-surgical SOC debridement followed by surgical debridement
- Gel Vehicle debridement followed by surgical debridement

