As an additional analysis, time to complete eschar removal will be compared between NexoBrid and Gel Vehicle using the same explanatory variables as for the main analysis of this endpoint.

11.1.3.3. *Blood loss*

In Section 10.3.3.3 two blood loss estimates are defined. Analyses with both blood loss estimates will be conducted. However, some missing values are expected. The analysis with less missing values will be regarded as more reliable and is therefore considered the main analysis. The other analysis is considered supportive. Both analyses will be conducted as follows:

The measure of blood loss defined in Section 10.3.3.3 will be computed for each patient, and the distribution in the NexoBrid group will be compared with that in the SOC group. Means, standard deviations, medians, and interquartile ranges will be calculated and presented as in Table 4. Furthermore, the blood loss will be described graphically by histograms. The normality of the data will be tested on each treatment group using the Shapiro-Wilk test. If the normal distribution hypothesis is not rejected at the 5% significance level in either group, then differences in distribution between NexoBrid and SOC will be tested using a t-test. If the normal distribution hypothesis is rejected either in the NexoBrid group or in the SOC group, then the

differences in distribution between the treatment groups will be tested using a Mann-Whitney test. The test results will be presented as in Table 7.

As sensitivity analysis, the procedure outlined above will be repeated using the PP instead of the FAS as analysis population.

Supportive analyses will include adjustments for the covariates overall TW depth (all TWs full thickness, mixed TWs, all TWs deep partial thickness), "Total %TBSA per patient", center group (as defined in Section 11.1.10), number of TWs (1, 2, ≥ 3) and number of debridement procedures. This will be done by including these variables in a regression model for blood loss together with treatment group.

If any of the baseline factors, gender, age, or percent SPT area (the area of SPT as a percentage of the total area of all TWs, classified as $<25\%$ or $\geq 25\%$), time from injury to randomization are found to be significantly different between the treatment groups, then the factor will be included as an extra adjusting covariate in a supportive analysis of blood loss (as described in the preceding paragraph).

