As an additional analysis, blood loss will be compared between NexoBrid and Gel Vehicle without covariate adjustment (similar to the main analysis of this endpoint).

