11.1.10. Stratification

The following factors are used to stratify the study design:

A. Total TBSA % per patient

A1: Total TBSA <=15%

A2: Total TBSA >15%

B. Overall depth per patient

B1: All TWs are full thickness;

B2: Mixed TWs – full thickness and deep partial thickness

B3: All TWs are deep partial thickness.

C. Center Group, to address possible differences in SOC procedures between sites (if any), to allow comparison of the results within group of centers and to reduce the likelihood of a group of centers including patients in only one arm of the study (5 groups of centers were formed based on similarity of SOC practice).

These factors are accounted for in the analyses of the primary and secondary endpoints by including them as adjusting variables.

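### The supportive NexoBrid versus SOC blood-loss regressions adjust for the post-randomisation number of debridement procedures, so no planned pooled model adjusts for baseline factors alone

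*SAP*

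**What the plan says.** SAP 11.1.3.3 compares blood loss between NexoBrid and SOC by a t-test, or by a Mann-Whitney test if normality is rejected in either arm. Neither uses covariates, and the same section describes the NexoBrid versus Gel Vehicle comparison as "without covariate adjustment (similar to the main analysis of this endpoint". 

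Two supportive regressions follow. The first adjusts for overall target-wound depth, total %TBSA, center group, number of target wounds "and number of debridement procedures. This will be done by including these variables in a regression model for blood loss together with treatment group". The second applies only if gender, age, SPT share or time from injury to randomisation differs significantly between arms. It adds that factor to the model of the preceding paragraph, so it contains the count as well. Both actual blood loss (ABL) measures go through the same scheme.

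For the procedure-wise measure, 10.3.3.3.1 says: "The ABL will be summed over all procedures carried out to remove eschar, with the Hb measured immediately before each procedure". The second measure treats the whole debridement period as one procedure.

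On how procedures arise:
- 7.1.1.2 lets the burn specialist repeat SOC procedures until debridement is complete.
- 7.1.2.1 makes a second NexoBrid application depend on the response to the first, and "NexoBrid may only be applied twice to the same burn wound area".
- One course listed in 10.3.3.3.5 is "NexoBrid debridement followed by non-surgical SOC debridement followed by surgical debridement".
- A footnote to the flow chart in 7.2 says: "A whole period of continuous dressing changes (from first coverage application to last coverage application) is considered as one non-surgical procedure".
- 9.2 gives the planned excision rates: "We therefore take the anticipated proportion with complete excision to be: NexoBrid 0.24 and SOC 0.60".

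On the strata (TBSA, depth, center group), 11.1.10 says: "These factors are accounted for in the analyses of the primary and secondary endpoints by including them as adjusting variables". Section 11.1.7 says the same for center only.

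**The concern.** The second objective in 2.2 concerns blood loss tied to the surgical burden. That is a total effect, and it includes whatever NexoBrid saves by avoiding operations. The number of procedures lies on that path. Holding it fixed removes part of the effect, and it also compares patients who reached the same count by different routes. One topical application followed by an excision, and two excision sessions, are both a count of two, but they need not bleed alike.

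Two forces pull the count in opposite directions. NexoBrid is expected to need less excision, which lowers its count. Its applications come before any SOC step and may be repeated, which raises its count. The SAP does not say which force is larger, so the direction of the bias is unknown in advance.

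At stake is the use of the supportive estimates. A reader will go to them to see whether the main result survives adjustment for wound depth, burn size and center. They cannot answer that question if the coefficient has also been conditioned on a consequence of treatment.

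**Working it through.** **Is there another pooled, baseline-adjusted comparison?** The per-protocol repeat in 11.1.3.3 uses the unadjusted procedure. The subgroup analyses in 11.1.11 use t-tests within levels of SPT share, TBSA and depth. The hematocrit and hemoglobin analyses (11.1.5.6, 11.1.5.7) use one-way analysis of variance. No pooled NexoBrid versus SOC blood-loss model adjusts for baseline factors alone.

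**Figures in the plan.** The SAP states no blood-loss effect, SD or power; 9.1 rests on the primary and two other secondary endpoints. The one usable input is in 9.2, and it reproduces: 0.40 − 0.072/2 = 0.364, about 0.36, and 0.60 − 0.24 = 0.36.

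**Effect of adding the count.** With equal arms and a model containing only treatment and count k:

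adjusted coefficient = D − b × d

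Here D is the true mean difference in loss (NexoBrid − SOC), d is the difference in mean count, and b is the pooled within-arm slope, that is the sum of within-arm covariances of loss and k divided by the sum of within-arm variances of k. All mL values and procedure patterns below are assumptions; only 0.24 and 0.60 come from the SAP.

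*Pattern 1: every patient has one topical or dressing step first, and excised patients then have one session of 400 mL; other procedures cost 0 mL.*
- D = 400 × (0.24 − 0.60) = −144 mL.
- d = 1.24 − 1.60 = −0.36, and b = 400.
- Adjusted: −144 − 400 × (−0.36) = **0 mL**. The real reduction vanishes.

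*Pattern 2: as pattern 1, but half of the excised SOC patients go straight to surgery.*
- d = 1.24 − 1.30 = −0.06.
- NexoBrid: variance 0.24 × 0.76 = 0.1824, covariance 400 × 0.1824 = 72.96.
- SOC: variance 0.30 × 0.70 = 0.21, covariance 400 × (0.30 × 2 + 0.30 × 1) − 1.30 × 240 = 48.
- b = 120.96/0.3924 = 308.3.
- Adjusted: −144 + 308.3 × 0.06 = **−125.5 mL**. Mild shrinkage.

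*Pattern 3: all excised SOC patients go straight to surgery.*
- Every SOC patient has k = 1, so d = 1.24 − 1.00 = +0.24, and b = 400 comes from the NexoBrid arm alone.
- Adjusted: −144 − 400 × 0.24 = **−240 mL**, 1.67 times the truth.

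*Pattern 4: as pattern 3, with a second NexoBrid application in 50% and a second surgical session in 20% of excised patients.*
- D = 400 × 1.2 × (−0.36) = −172.8 mL.
- d = (1 + 0.5 + 0.288) − (1 + 0.12) = 0.668.
- NexoBrid: number of sessions has mean 0.24 × 1.2 = 0.288 and variance 0.24 × (0.8 × 1 + 0.2 × 4) − 0.288² = 0.3011. Count variance is 0.3011 + 0.25 = 0.5511; covariance is 400 × 0.3011 = 120.42.
- SOC: count variance 0.12 × 0.88 = 0.1056; covariance 400 × (0.12 × 0.40 + 0.1056) = 61.44.
- b = 181.86/0.6567 = 277.0.
- Adjusted: −172.8 − 277.0 × 0.668 = **−357.8 mL**, 2.07 times the truth.

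*Pattern 4 with 50 mL per other procedure.*
- Other procedures average 1.5 on NexoBrid and 0.4 on SOC, so D = −172.8 + 50 × 1.1 = −117.8 mL.
- The covariances become 120.42 + 50 × 0.25 = 132.92 and 61.44 − 50 × 0.048 = 59.04, so b = 191.96/0.6567 = 292.3.
- Adjusted: −117.8 − 292.3 × 0.668 = **−313.1 mL**, 2.66 times the truth.

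**Cross-check by simulation.** This used 75 per arm, 600 mL per surgical session, 30% second sessions and residual SD 300 mL, with TBSA as a baseline covariate. When every patient had one non-surgical step first, adding the count moved the baseline-adjusted difference from −283 to −1 mL, and rejection fell from 92% to 5%. When 60% of excised SOC patients went straight to surgery, 30% of NexoBrid patients had a second application and other procedures cost 50 mL, it moved from −248 to −334 mL.

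**The strata wording, main analysis by main analysis:**

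| Main analysis | TBSA | Depth | Center group |
|---|---|---|---|
| Primary, Fisher's exact test (11.1.2) | no | no | no |
| Surgical excision (11.1.3.1) | yes | yes | supportive only |
| Time to eschar removal, Cox model (11.1.3.2) | yes | yes | yes |
| Blood loss (11.1.3.3) | no | no | no |

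Only one of the four fits 11.1.10 as it is worded.

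**The case against.** The strongest reply is that these models are only supportive. The confirmatory test is unadjusted, estimates the total effect and is valid under randomisation; blood loss comes last in the hierarchy; and the second model may never be run. All of that stands and limits the reach of the point. It does not make the coefficient a useful check on the main result.

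The subgroup t-tests do condition on baseline factors. They are exploratory and give separate within-stratum results, so they do not replace a pooled adjusted estimate.

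The sizes rest on invented mL values and procedure patterns. The result depends heavily on how often SOC patients have a dressing period before excision: patterns 1 and 3 differ in nothing else. A reader might infer that the adjustment favours NexoBrid, or that it works against it. The SAP supports neither reading.

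The footnote in 7.2 concerns when assessments are repeated, and the SAP does not say that it defines this covariate. That the arms count procedures differently is therefore an inference. The point does not need it: the count is post-randomisation and can respond to treatment under any counting rule. The same holds for the whole-period blood-loss measure, which is not itself a sum over procedures.

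Finally, 11.1.7 and 11.1.10 speak of analyses, not main analyses, and can be read as met by the supportive models. That reading is fair.

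**Conclusion.** The concern holds for the supportive models. Both condition on a post-randomisation count that treatment can change, and no planned pooled NexoBrid versus SOC blood-loss model adjusts for baseline factors alone. In the patterns worked above the adjusted coefficient ran from 0 to about 2.1 times the true difference with no loss at other procedures, and to about 2.7 times with 50 mL each. This shows that the bias can go either way and can be large. It does not predict its value in this trial, because everything except the two excision rates is assumed.

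Two stronger readings are not supported. A reader might infer that the main blood-loss test is biased or that the type I error of the hierarchy is at risk; neither follows, since the main test does not use the count. A reader might also infer from 11.1.7 and 11.1.10 that the main test is undefined or must be adjusted. Section 11.1.3.3 fixes it clearly as unadjusted, and that is a valid choice. What remains there is a minor mismatch of wording.

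**What to change.** In 11.1.3.3, delete the number of debridement procedures from the supportive between-arm models. The first model then contains treatment, overall target-wound depth, total %TBSA, center group and number of target wounds. The second adds any imbalanced baseline factor.

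Tabulate the number of procedures by arm. If a model with the count is still wanted, keep it separate, label it exploratory, and state that its treatment coefficient is not read as the treatment effect.

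In 11.1.7 and 11.1.10, state which main analysis adjusts for which strata: none for the primary and blood-loss tests, depth and TBSA for excision with center supportive, and all three for time to eschar removal.

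The cost is SAP wording only, since every covariate is already collected. The change should be made before unblinding, because a baseline-only model chosen afterwards would be post hoc.
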